Clinical Development

MIJ821

CMIJ821A12201 / NCT04722666

A double-blind, placebo-controlled, randomized dose-ranging trial to investigate efficacy and safety of intravenous MIJ821 infusion in addition to comprehensive standard of care on the rapid reduction of symptoms of Major Depressive Disorder in Subjects who have suicidal ideation with intent

Statistical Analysis Plan (SAP)

Document type: SAP
Document status: Amendment v1 Final
Release date: 30-Jun-2023
Number of pages: 55

Property of Novartis
For business use only
May not be used, divulged, published or otherwise disclosed
without the consent of Novartis
Template Version 3.0, Effective from 01-Jul-2020

Document History – Changes compared to previous final version of SAP

Date	Major updates and reason	Section and title impacted (Current)
14-Jun-2021	First version	
30-Jun-2023	Amendment 1 final	
	Added MIJ821 PK analysis in CSR SAP since it's one of secondary endpoints	Section 2.1.3 Analysis sets Section 2.7 PD and PK/PD analyses
	Defined Randomized Set for population description; defined Extension Set for follow-up data analysis	Section 2.1.3 Analysis sets
	For the supplementary estimand, changed the missing data imputation approach from J2R to MAR under treatment policy. Because MIJ821 will sustained effect after 1st dosing for a while, so J2R is scientifically inappropriate.	Section 2.4.5 Supplementary analysis
	Removed summary of MADRS, [REDACTED]	Section 2.4.6 Supportive analysis Section 2.10.1 Effect on depression mood Section 2.10.2 Effect on suicidality
	Added KM analysis for time to relapse;	Section 2.5.2 Statistical hypothesis, model, and method of analysis
	Added logistic regression model with firth method as the alternative model to repeated logistic regression model if not converged due to zero count	Section 2.10.2 Effect on suicidality

Date	Major updates and reason	Section and title impacted (Current)
	Added the summary of time to onset and time to resolution for AESIs if onset on dosing day, and since most recent dose.	Section 2.6.1.1 Adverse events (AEs)
	Added the change from most recent dose in terms of ECG parameters; Removed summary for holter due to data is not supportive for it	Section 2.6.4.1 ECG and cardiac imaging data
	Added the change from most recent dose for SBP/DBP	Section 2.6.4.2 Vital Signs
	[REDACTED]	[REDACTED]
	[REDACTED]	[REDACTED]
	[REDACTED]	[REDACTED]
	[REDACTED]	
	[REDACTED]	
	[REDACTED]	
	[REDACTED]	
	[REDACTED]	[REDACTED]
	[REDACTED]	[REDACTED]

Table 5-3	Liver Abnormality Criteria	52
Table 5-4	Renal Abnormality Criteria.....	53
Table 5-5	ECG Abnormality Criteria	53
Table 5-6	Vital Signs Abnormality Criteria	54

List of figures

28

List of abbreviations

AE	Adverse Event
AESI	Adverse Event of Special Interest
ALP	Alkaline Phosphatase
ALT	Alanine Aminotransferase
ANCOVA	Analysis of Covariance
AST	Aspartate Aminotransferase
ATC	Anatomical Therapeutic Chemical
AUC	Area Under the Curve
BDNF	Brain-Derived Neurotrophic Factor
BP	Blood Pressure
BPIC-SS	Bladder Pain/Interstitial Cystitis Symptom Score
CMH	Cochran-Mantel-Haenszel
CRF	Case Report Form
CRO	Contract Research Organization
CRS	Case Retrieval Strategy
CSR	Clinical Study Report
CTT	Clinical Trial Team
CV	Coefficient of Variation
DBP	Diastolic Blood Pressure
DBS	Deep brain stimulation
DMC	Data Monitoring Committee
DR	Dose Response
ECT	Electroconvulsive therapy
ECG	Electrocardiogram
ENS	Extension Set
FAS	Full Analysis Set
IA	Interim Analysis
IRT	Interactive Response Technology
LLOQ	Lower Limit of Quantification
LoE	Lack of Efficacy

MADRS	Montgomery–Asberg Depression Rating Scale
MAOIs	Monoamine Oxidase Inhibitors
MAR	Missing At Random
MCP-Mod	Multiple Comparison Procedure-Modelling
MDD	Major Depression Disorder
MDE	Major Depressive Episode
MedDRA	Medical Dictionary for Regulatory Activities
MMRM	Mixed-effects Model for Repeated Measures
NMDA	N-Methyl-D-Asparate
PD	Pharmacodynamic(s)
PD	Protocol Deviation
PK	Pharmacokinetic(s)
PKS	PK Analysis Set
PoC	Proof of Concept
PRO	Patient Reported Outcomes
PT	Preferred Term
QTcF	QT interval corrected by Fridericia's formula
RAS	Randomized Set
RTS	Retreatment Set
S-STS	Sheehan Suicidality Tracking Scale
SAE	Serious Adverse Event
SAF	Safety Set
SAP	Statistical Analysis Plan
SBP	Systolic Blood Pressure
SD	Standard Deviation
SMQ	Standardized MedDRA Query
SNRI	Serotonin-norepinephrine reuptake inhibitor
SoC	Standard of Care
SOP	Standard Operating Procedure
SSRI	Selective serotonin-reuptake inhibitor
TCA	Tricyclic antidepressant
TEAEs	Treatment-Emergent Adverse Events
TFL	Tables, Figures and Listing
TMS	Transcranial Magnetic Stimulation
VNS	Vagus nerve stimulation
WHO	World Health Organization

1 Introduction

The purpose of this statistical analysis plan (SAP) is to provide details of the statistical analysis according to Section 12 of the study **Protocol v01** for MIJ821A Study CMIJ821A12201 dated **Jun 01, 2021** and along with any additional analyses, specifications or deviations from the protocol planned.

The scope of this plan includes the primary, secondary, [REDACTED], which will be executed by Novartis internal statisticians and programmers, if not specified differently. Those analyses will be reported in the CSR.

1.1 Study design

This is a Phase 2b double-blind, placebo-controlled, randomized, parallel-group dose-ranging trial to investigate the efficacy and safety of four doses of intravenous MIJ821 administered as 40-min infusion in addition to comprehensive standard of care (SoC) for the rapid reduction of the symptoms of major depression disorder (MDD) in participants who have suicidal ideation with intent. Comprehensive SoC includes initial hospitalization and pharmacological antidepressant therapy (antidepressant monotherapy or an antidepressant plus augmentation). In addition, the study will also explore the effect for single dose administration of 0.16 mg/kg and 0.048 mg/kg given once to treat MDD in participants who have suicidal ideation with intent.

Participants meeting the eligibility criteria will be randomized in a 2:1:2:2:2:2 ratio to treatment with:

- placebo every other week
- MIJ821 0.0048 mg/kg every other week
- MIJ821 0.016 mg/kg every other week
- MIJ821 0.048 mg/kg every other week
- MIJ821 0.16 mg/kg every other week
- MIJ821 0.048 mg/kg single infusion with two subsequent placebo dosages given every other week
- MIJ821 0.16 mg/kg single infusion with two subsequent placebo dosages given every other week

on top of ongoing pharmacological antidepressant SoC treatment. In all treatment arms, investigational treatment will be administered by intravenous infusion every other week, three infusions in total during the placebo-controlled double-blind Core, 6-week period of the study.

The study consists of three periods: a Screening Period (up to 48 hours), a Double-blind Core Period (6 weeks) and Extension Period (up to 52 weeks).

Approximately 195 participants will be randomized to Double-blind Core Period via Interactive Response Technology (IRT) in a blinded manner. There is no stratification factor considered in randomization.

After completing the Double-blind Core Period, all participants will enter the Extension Period for a minimum of 8 weeks and a maximum of 52 weeks. Participants who complete the Core Period on study treatment (with Day 29 infusion completed) and are classified as responder or

remitters at the end of Core Period, will be eligible for a retreatment course of 6 weeks in case of relapse. The details are defined in protocol Section 3.2 and 3.3.

The primary analysis will be performed at end of Core Period and at the end of study. There will be an unblinded interim analysis (IA) performed when all participants completed the 2 weeks follow-up visit post Core Period. The purpose of this IA is to select the optimal dose of MIJ821 for Phase 3.

1.2 Study objectives and endpoints

Table 1-1 Objectives and Related Endpoints

Objective(s)	Endpoint(s)
Primary objective(s)	Endpoint(s) for primary objective(s)

• Core: To investigate dose response relationship for 4 doses of MIJ821 vs. placebo	
• Change from baseline in MADRS total score at 24 hours after the start of the first infusion
Secondary objective(s)	Endpoint(s) for secondary objective(s)

• Core: To assess safety and tolerability of MIJ821	
• Number and severity of treatment-emergent adverse events (TEAEs), including AEs of special interest in Core Period

• Core and Extension: To assess the effect of MIJ821 on sustained response and remission	
• Proportion of participants meeting response criteria ($\geq 50\%$ reduction from baseline in MADRS total score) over time in Core Period.• Proportion of participants meeting criteria for sustained response ($\geq 50\%$ reduction from baseline in MADRS total score sustained for a period of at least four weeks) in Core Period• Proportion of participants meeting remission criteria (MADRS total score of ≤ 12) over time in Core Period• Proportion of participants meeting criteria for sustained remission (MADRS total score of ≤ 12 sustained for a period of at least four weeks) in Core Period• Proportion of participants meeting criteria for relapse over all randomized population over fixed period in Extension Period• Proportion of relapsing participants meeting response criteria or remission criteria after the first infusion of MIJ821 retreatment in Extension Period

• Core and Extension: To assess MIJ821 pharmacokinetics in plasma	
• PK parameters of MIJ821 in plasma after 1st infusion described by AUClast, Cmax, Tmax (parameters not limited) and after each infusion described by Cmax and Tmax

Objective(s)	Endpoint(s)

Objective(s)	Endpoint(s)

1.2.1 Primary Estimand(s)

The primary clinical question of interest is: what is the effect of the MIJ821 versus placebo in conjunction with pharmacological SoC on change from baseline in MADRS total score at 24 hours post first dose administration, in patients with MDD who have suicidal ideation with intent, accounting for intercurrent events with potential confounding effects and intercurrent events leading to study discontinuation prior to the 24 hours assessment.

The primary estimand is described by the following attributes with further details in [Section 2.4.1](#):

- Population: Patients with MDD who have suicidal ideation with intent.
- Endpoint: change from baseline in MADRS total score at 24 hours post first dose administration
- Treatment of interest: the randomized treatment (MIJ821 0.0048 mg/kg, 0.016 mg/kg, 0.048 mg/kg, 0.16 mg/kg or Placebo, 40 min IV infusion) add-on to SoC. Dose titration or adjustments of SoC antidepressant treatment allowed during the first 2 weeks of double-blind treatment, if needed, with dosages maintained thereafter during the core treatment phase.
- Handling of intercurrent events prior to MADRS assessment at 24 hours:
 - Intake or change in concomitant medications/therapies other than SoC which have potential confounding effects: hypothetical strategy
 - Intake of prohibited medications/therapies: hypothetical strategy
 - Intake of rescue medications: hypothetical strategy
 - Intercurrent events related to pandemic: hypothetical strategy
 - Intercurrent events leading to study discontinuation due to Adverse events (AEs), lack of efficacy or other reasons: treatment policy strategy
- The summary measure: difference in variable means between treatments

2 Statistical methods

2.1 Data analysis general information

This document describes the analysis plan for unblinded IA at the end of Core Period and the final analysis at the end of study. When the last participant completed 2 weeks' follow-up visit (Day 57), data collected up to the cutoff date will be included at the unblinded IA. The main analysis of unblinded IA will focus on Core Period as well as time to relapse in Extension Period.

At end of the study, data collected mainly from Extension Period will be analyzed. The full scope of analysis will be performed by Novartis.

The analysis for the requirement of regular Data Monitoring Committee (DMC) meetings will be performed by an independent statistical analysis team outside of Novartis (CRO). The process is detailed in the DMC Charter and a separated SAP for DMC.

Statistical analysis will be performed using SAS® statistical software (SAS Institute, Cary, NC, USA.) version 9.4 or higher, and R version 3.5.3 or higher.

Unless otherwise specified, summary tables/listings/figures will be presented for each treatment arm in the respective analysis set. The pooling analysis of treatment arms is defined in [Section 2.4.1](#). In general, data of interest will be listed by treatment arm and by country/center number/subject id (/period/visit wherever applicable). Summary tables and figures by visit will be displayed for Core Period and Extension Period separately. For participants who are retreated during Extension Period, data under Retreatment Period will be analyzed and displayed separately (see definition in [Table 2-1](#)).

In general, assessments at scheduled visits will be analyzed. The assessment schedule is defined in protocol Table 8-1 and Table 8-2, thus will not be repeated in this SAP.

Categorical data will be presented as frequencies and percentages. For continuous data, the number of non-missing observations, mean, standard deviation (SD), median, minimum and maximum will be presented.

General information on treatment arm handling, decimal places and other output-related information will be specified in tables, figures and listing (TFLs) shells accompanying this analysis plan.

2.1.1 General definitions

Study drug (treatment)

Study drug (treatment) referred in this document will be MIJ821 or Placebo.

Randomization (Enrollment) Date

Randomization (Enrollment) Date is the date on which a participant is assigned to one of the treatments through IRT in Core Period.

Date of first dose

The date of first dose is the date on which a participant is administered the first infusion of study drug, which maybe on the same day or after the randomization date. For participants who are randomized but never dosed with double-blind study drug after randomization, the date of first dose is considered missing.

Date of last dose

The date of last dose is the latest infusion date throughout study, including Extension Period for participants who take retreatment for relapse.

Day 1

Day 1 is defined as the first dose date. For participants who are randomized but not dosed after randomization, the Study Day 1 is defined as the date of randomization.

Study day

Study Day is defined as the number of days from Study Day 1.

Before Study Day 1:

Study Day = (Date of Interest – Date of Study Day 1)

On or after Study Day 1:

Study Day = (Date of Interest – Date of Study Day 1) + 1

Therefore the day prior to Study Day 1 is -1.

Day(s) since start of retreatment is defined as the number of days from the first dose date of retreatment. It will be calculated for assessments performed during retreatment period by

Date of interest – Date of first dose of retreatment + 1

Baseline

A baseline value refers to the last evaluable measurement prior to the first dose, irrespective of re-screening. In this case, baseline values will be the values obtained predose on first dosing day or on an earlier visit (scheduled or unscheduled) which is the closest to the first dosing day, if the assessment was not done on the first dosing day. In case of multiple assessments on the same day, the last valid one will be considered.

Baseline of Retreatment

For participant who take retreatment during Extension Period, the baseline for retreatment assessments will be the last evaluable measurement prior to the first dose of retreatment. It will be the measurement obtained predose on the first day of retreatment, or the last valid assessment which is closest to start of retreatment.

2.1.2 Analysis period and visit remapping

All study data of participants will be grouped into Core Period and Extension Period according to [Table 2-1](#). For those who take retreatment for relapse, assessments during retreatment will be grouped into Retreatment Period specially.

Table 2-1 Analysis Period for Data

Analysis Period	Start Time Point	End Time Point
Core Period	Day 1	For participant who won't join in Extension Period: Date of End of study visit; For participant who join in Extension Period: End of Core visit (Day 43)
Extension Period	For participant who join in Extension Period: Date of End of Core visit + 1	For participant who join in Extension Period: Date of End of Study visit
Retreatment Period	For participant who take retreatment: Date of first dose of retreatment	For participant who take retreatment: Date of last Retreatment visit

Analysis visit and windows

Since the actual visit for a participant may not exactly coincide with their targeted visit date, the actual visit date will be mapped to an analysis visit for the purpose of data summary and model analysis. However for assessments (except for PK sampling) performed at -2 hours, -1 hour, 20 min, 40 min, 2 hours, 4 hours on the same day, there is no need to remap visit time, so site collected timepoint will be analysed.

The visit window in [Table 2-2](#) defines the analysis visit applicable for assessments in Core Period and Extension Period, including efficacy endpoints (e.g. MADRS, [REDACTED]), safety endpoints (e.g. laboratory, vital signs, ECG, [REDACTED]).

Table 2-2 Analysis Visit Windows for Core Period and Extension Period

Analysis Period	Study Visit	Target Day/Time	Study Day
Core Period	Baseline	Day 1 -2 hours predose (See definition for baseline in Section 2.1.1)	-2, - 1, 1 (predose)
	D1 20 min, 40 min, 2 h, 4 h	Day 1 20 min, 40 min, 2 hours, 4 hours post dose	1 (post dose)
	24 h	2	2
	D8	8	3 - 11
	D15 -2 h, -1 h, 40 min, 2 h, 4 h	Day 15 -2 hours, -1 hour predose, 40 min, 2 hours, 4 hours post dose	12 - 18
	D22	22	19 - 25
	D29 -2 h, -1 h, 40 min, 2 h, 4 h	Day 29 -2 hours, -1 hour predose, 40 min, 2 hours, 4 hours post dose	26 - 32
	D36	36	33 - 39
	D43	43	40 – End of Core Visit
Extension Period	2 weeks follow-up	57	(End of Core Visit + 1) - 64
	4 weeks follow-up	71	65 - 85
	Monthly follow-up post Day 43	43 + (n)*28 n is the nth month follow up	(-13, +14) of target day The last follow-up visit will last until the end of study

The main analyses will summarize data collected in Core Period up to 2 weeks follow up in Extension Period. The monthly follow-up visit in Extension Period will not be presented in by-visit summary, unless otherwise specified.

In addition for participants who are retreated during Extension Period, assessments performed during Retreatment Period will be mapped to the analysis visit according to [Table 2-3](#).

Table 2-3 Analysis Visit Windows for Retreatment Period

Analysis Period	Study visit	Target Day since start of retreatment*	Day since start of retreatment*
Retreatment Period	Baseline of Retreatment	Day 1 -2 hours pre-retreatment (See definition for	1

		baseline of retreatment in Section 2.1.1)	
	Retreatment D1 40 min, 2 h, 4 h	Day 1 40 min, 2 hours, 4 hours post retreatment	1
	Retreatment 24 h	2	2
	Retreatment D8	8	3 - 11
	Retreatment D15 -2 h, -1 h, 40 min, 2 h, 4 h	Day 15 -2 hours, -1 hour predose, 40 min, 2 hours, 4 hours post dose	12 - 18
	Retreatment D22	22	19 - 25
	Retreatment D29 -2 h, -1 h, 40 min, 2 h, 4 h	Day 29 -2 hours, -1 hour predose, 40 min, 2 hours, 4 hours post dose	26 - 32
	Retreatment D36	36	33 - 39
	Retreatment D43	43	40 – End of Retreatment Visit

* See the definition for Day(s) since start of retreatment in [Section 2.1.1](#)

When multiple assessments are mapped into the same window, following rules will be applied for efficacy and safety endpoints (except ECG) and PROs:

When assessments for scheduled visit and unscheduled visit are both present within the same window, the scheduled assessments value should be used. Unscheduled visit will only be used when there is no measurement from the scheduled visit in the defined window. Two special cases need to be handled as following rule:

- When assessments on a dosing day drop to the window of a non-dosing visit, for example the dosing on Day 15 was delayed to the window of Day 22, the pre-dose assessment will be mapped to the non-dosing visit of Day 22, while the post-dose assessment will not be mapped. Unless scheduled assessments for Day 22 were performed, the scheduled ones should be mapped then.
- When assessments on non-dosing day drop to the window of a dosing visit, for example the visit Day 8 was delayed to Day 15 and no dosing was administered, assessments will be mapped to the pre-dose hour of this dosing visit. Unless the dosing were administered and scheduled assessments performed within the window, the scheduled assessments should be mapped then.

In case of multiple assessment values among the same type of visit (i.e. two unscheduled assessments) within the same analysis window, the closest to the scheduled visit day will be used. In case of equal distances (e.g same day), the latest assessment value will be used. The exception is an assessment at early study withdrawal visits along with another assessment within a window. In such cases, the early-withdrawal assessment will be used.

For ECG, the same strategy will be applied except that no prioritization of scheduled vs unscheduled visit will be made.

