#### **Post dose blood pressure monitoring:**

The following monitoring criteria based on post-dose blood pressure assessments during the dosing phase should be followed:

[figure not shown]
At 2 hours postdose, if the SBP is  $\geq 160$  mmHg and/or the DBP  $\geq 100$  mmHg, assessments should continue every 30 minutes until:

- The blood pressure is <160 mmHg SBP and <100 mmHg DBP, or
- In the investigator's clinical judgment, the subject is clinically stable or
- The subject is referred for appropriate medical care, if clinically indicated.
- If the blood pressure remains  $\geq 160$  mmHg SBP and/or  $\geq 100$  mmHg DBP, 4 hours after dosing, the subject should be referred for immediate medical treatment.

For patients with SBP  $\geq 180$  mmHg but <200 mmHg and/or the DBP is  $\geq 110$  mmHg but <120 mmHg, further dosing should be interrupted (no subsequent IV infusion given) and the subject should be referred to a cardiologist, or other specialist for a follow-up assessment.

After the assessment by a cardiologist, or other specialist, if recommended by the referring doctor and considered appropriate according to the clinical judgment for the subject to continue in the study, the subject may continue with further dosing only if the predose blood pressure at the next scheduled visit is within the acceptable range.

All follow-up information and procedures performed must be recorded as appropriate in the CRF.

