### **Clinical laboratory evaluations**

Summary statistics will be provided by visit/time point and treatment. Shift tables using the low/normal/high/ (low and high) classification based on predefined limits will be used to compare baseline to the worst on-treatment value. Notable abnormal laboratory data will be listed by treatment group, participant, and visit if limits are available.

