**Table 16-3 Follow up requirements for liver laboratory triggers with liver symptoms**

ALT	TBL	Liver Symptoms	Action
ALT increase without bilirubin increase:			
If normal at baseline: ALT > 3 x ULN	Normal	None	
 
• No change to study treatment
 
• Measure ALT, AST, ALP, GGT, TBIL, INR, albumin, CK, and GLDH in 48-72 hours.
 
• Follow-up for symptoms.
 

If elevated at baseline: ALT > 2 x baseline or > 300 U/L (whichever occurs first)	For patients with Gilbert's syndrome: No change in baseline TBL		
If normal at baseline: ALT > 5 x ULN for more than two weeks	Normal	None	
 
• Interrupt study drug
 
• Measure ALT, AST, ALP, GGT, TBIL, INR, albumin, CK, and GLDH in 48-72 hours.
 
• Follow-up for symptoms.
 
• Initiate close monitoring and workup for competing etiologies.
 
• Study drug can be restarted only if another etiology is identified and liver enzymes return to baseline.
 

If elevated at baseline: ALT > 3 x baseline or > 300 U/L (whichever occurs first) for more than two weeks	For patients with Gilbert's syndrome: No change in baseline TBL		
If normal at baseline: ALT > 8 x ULN	Normal	None	
ALT increase with bilirubin increase:			
If normal at baseline: ALT > 3 x ULN	TBL > 2 x ULN (or INR > 1.5)	None	
If elevated at baseline: ALT > 2 x baseline or > 300 U/L (whichever occurs first)	For patients with Gilbert's syndrome: Doubling of direct bilirubin		
If normal at baseline: ALT > 3 x ULN	Normal or elevated	Severe fatigue, nausea, vomiting, right upper quadrant pain	
If elevated at baseline: ALT > 2 x baseline or > 300 U/L (whichever occurs first)			

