2.6.4.2 Vital signs

[figure not shown]
The change from baseline of vital signs (systolic/diastolic blood pressure, pulse rate, temperature) and weight will be summarized by treatment arm and by analysis visit, for Core Period up to 2 weeks' follow up visit, and separately for the Retreatment Period.

[figure not shown]
In addition, for systolic/diastolic blood pressure, the change from most recent dose will be summarized in a similar manner.

For Core Period up to 2 weeks follow up visit, the mean (SD) of change from baseline will be displayed by line plot. The change from the each dose up to 2 weeks will be plot in the same manner.

The proportion of any clinical relevant abnormality postbaseline and break donw by visit will be summarized and presented in listing at individual level.

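### The SAP's one-value-per-window rule can omit peak values from by-visit safety abnormality counts, leaves the other abnormality counts undefined, and the protocol's worst-value laboratory shift has gone without being declared

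*SAP*

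**What the plan says.** **Selection rule.** SAP 2.1.2 states its scope as "following rules will be applied for efficacy and safety endpoints (except ECG) and PROs". Within a window, "Unscheduled visit will only be used when there is no measurement from the scheduled visit in the defined window". Among readings of the same type, the one closest to the scheduled day is taken, and then "In case of equal distances (e.g same day), the latest assessment value will be used". An early-withdrawal assessment overrides these steps. On ECG the SAP says: "For ECG, the same strategy will be applied except that no prioritization of scheduled vs unscheduled visit will be made". SAP 2.1 adds that, in general, scheduled visits are analysed. Nominal time points on dosing days (20 min, 40 min, 2 h, 4 h) are kept as the site recorded them.

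**Abnormality counts.**
- SAP 2.6.3 gives new or worsening laboratory abnormalities by arm and analysis visit. Its liver and renal counts have their own lead-in and refer to any abnormality under Tables 5-3 and 5-4.
- SAP 2.6.4.1 gives ECG abnormalities (Table 5-5) by arm and analysis visit.
- SAP 2.6.4.2 gives "The proportion of any clinical relevant abnormality postbaseline", with a breakdown by visit.

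**Repeats ordered by the protocol.** If blood pressure is at least 160 systolic or 100 diastolic at 2 h, "assessments should continue every 30 minutes until" it settles (Protocol 10.2.3). After a liver trigger the instruction is "Measure ALT, AST, ALP, GGT, TBIL, INR, albumin, CK, and GLDH in 48-72 hours" (Protocol Table 16-3). Renal findings are to be confirmed between 24 hours and 5 days later (Protocol 10.2.2).

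**Worst value.** Protocol 12.5.2 planned laboratory shift tables that "will be used to compare baseline to the worst on-treatment value". SAP 2.6.3 has no shift table, and SAP Section 4 declares no change to protocol analyses.

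**The concern.** One value per window is a sound convention for by-visit means and repeated-measures models. It is a poor one for asking whether a participant ever crossed a threshold, because neither closest nor latest takes account of severity. The protocol orders extra readings because a value was abnormal, and these are the readings that give way to a scheduled value.

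Tables 5-3 to 5-6 hold the thresholds that describe tolerability, such as ALT above 5 or 8 times the upper limit, QTcF above 500 msec, and systolic pressure above 180 or at least 200 mmHg. Protocol 4.4 and SAP 2.11 make safety one of the inputs to the choice of Phase 3 dose. That analysis is run unblinded by the study team, so the choice of readings should be fixed in the text beforehand.

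**Working it through.** The documents give no figure to reproduce. The check has four steps.

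**1. Direction.** The values kept by the rule are a subset of all readings. The number of participants who ever cross a threshold on kept values is therefore at most the number who cross it on all readings. The rule can lower such a count but never raise it.

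**2. Do triggered laboratory repeats meet a scheduled value?** Inputs: the windows in SAP Table 2-2 (24 h: Day 2; D8: 3-11; D15: 12-18; D22: 19-25; D29: 26-32; D36: 33-39; D43: 40 to End of Core; 2-week follow-up: to Day 64). Assumptions: every visit is on its target day, End of Core is Day 43, and each of the seven visits from 24 h to D43 can be a trigger. Repeat day = trigger day + lag.

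| Repeat | Lags (days) | Repeat days | In trigger visit's own window | In the next visit's window |
|---|---|---|---|---|
| Liver | 2, 3 | 7 × 2 = 14 | 5 × 2 = 10 | 4 |
| Renal | 1 to 5 | 7 × 5 = 35 | 5 × 3 = 15 | 20 |

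The five visits D8 to D36 supply the own-window repeats; for example, Day 22 + 3 = Day 25, inside 19-25. Repeats after 24 h fall in the D8 window. Repeats after Day 43 fall in the follow-up window, where a Day 45 repeat loses to the scheduled Day 57 value. The protocol plans blood chemistry weekly in the Core Period, so a scheduled value is normally present. When it is, the repeat is not used.

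**3. Which counts can change?**
- *New or worsening laboratory abnormality (by visit).* The bar is the normal range or, if baseline was abnormal, the baseline value. A repeat prompted by a scheduled value that is already counted changes nothing for that parameter. What can be lost is an abnormality seen only at an unscheduled visit, or another item of the repeat panel (say bilirubin) that first leaves its range on the repeat.
- *ECG (by visit).* Suppose QTcF is 505 msec at 24 h and 497 msec on a same-day repeat. The latest is used, so the flag above 500 msec is lost. Nominal dosing-day time points are protected, so this applies mainly to non-dosing visits.
- *Vital signs (visit breakdown).* Repeats at 2.5, 3.0 and 3.5 h match no nominal time point. In the proof-of-concept study the mean placebo-adjusted rise peaked between 2 and 4 h (Protocol 4.5). A sequence of 170, 185, 165 mmHg at 2, 3 and 4 h would show no value above 180. If dosing is delayed into a non-dosing window, post-dose assessments are not mapped at all.
- *Liver, renal and any-post-baseline vital signs.* Suppose ALT is 4 times the upper limit at scheduled Day 22 and 9 times on Day 25. If the count uses windowed values, the flags above 5 and 8 times are lost. If it uses all readings, they are kept. The text does not settle which.

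**4. Illustration of size for one dosing day (assumed inputs, not trial data).** Simulated baseline SBP has mean 125, SD 10, capped at 140. The individual peak rise is gamma distributed (shape 4) with mean 15, 20 or 30 mmHg. Peak time is uniform over 1.5-4 h, with a bell-shaped course of width 1.2 h. Reading noise has SD 3, 5 or 8 mmHg. Extra readings at 2.5, 3 and 3.5 h are taken whenever the 2 h value is at least 160. Percentage with any SBP above 180, scheduled readings only → all readings:

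| Mean rise | Noise SD 3 | Noise SD 5 | Noise SD 8 |
|---|---|---|---|
| 15 | 0.05 → 0.09 | 0.08 → 0.13 | 0.16 → 0.26 |
| 20 | 0.52 → 0.76 | 0.60 → 0.93 | 0.92 → 1.38 |
| 30 | 4.72 → 6.41 | 5.09 → 6.95 | 5.81 → 8.09 |

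Missed share = (all − scheduled) / all, from unrounded values: 26% to 41%. In an arm of 30, the largest gap is (0.0809 − 0.0581) × 30 = 0.68 participant. At a mean rise of 20 it is at most (0.0138 − 0.0092) × 30 = 0.14.

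**The case against.** A reader might infer that the SAP drops the triggered repeats from every threshold count. The text does not support that. The liver and renal counts are for any abnormality, Table 5-3 applies its criteria to each assessment, and the vital-sign count covers any time after baseline. None of these is expressly tied to a window. Nor does SAP 2.1 restrict analysis to scheduled visits; it says only that this holds in general.

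The triggering reading is also usually the scheduled one and is kept, so the first threshold is still counted. A flag is lost only if the repeat crosses a further threshold or the abnormality appears only at an unscheduled visit. The ECG example has a further limit: the protocol's discontinuation criterion requires QTcF above 500 msec to be confirmed by repeat, and 497 does not confirm it.

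Other routes remain. Abnormal values are listed, clinically significant findings are analysed as adverse events, and blood pressure changes and QT prolongation are events of special interest with their own summaries.

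Most of this stands, and it limits the point. It does not remove it. Listings give no incidence by arm, and adverse-event capture depends on a judgement of clinical significance. Table 5-5 sets its QTcF flag without a confirmation requirement. Where the SAP is silent, the general default is scheduled visits.

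**Conclusion.** The point holds in a limited form. For the counts expressly presented by analysis visit, the rule can omit a more extreme value seen only on a repeat or at an unscheduled visit. For the liver, renal and any-post-baseline vital-sign counts, under-counting is possible but not established. This rests on the readable SAP text; blacked-out parts could not be checked.

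The missing shift to the worst on-treatment laboratory value is a separate matter and does not depend on how the window rule is read: the protocol specifies it, the SAP lacks it, and no change is declared.

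The size cannot be derived from the documents. The simulation shows a gap below one participant per 30-person arm for one dosing day, even at its largest, and rests wholly on assumed inputs. Its 30 mmHg case goes beyond the proof-of-concept report of mean placebo-adjusted changes below 20 mmHg, although individual peaks can average more than the peak of a mean curve.

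A reader might also infer that the rule flattens the dose-related safety gradient, because higher doses would have more repeats. The documents do not show that repeats concentrate at any dose, so that conclusion is not available.

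**What to change.** 1. In SAP 2.1.2, limit the one-value-per-window rule to by-visit descriptive summaries and models.
2. For the participant-level incidence of abnormality under Tables 5-3 to 5-6, use the worst of all post-baseline values in the analysis period, scheduled or unscheduled. State this in SAP 2.6.3, 2.6.4.1 and 2.6.4.2. ECG, now counted only by visit, would gain an any-time row.
3. Give the scheduled-only count as a footnote, because participants with more repeats have more chances to cross a threshold.
4. Restore the shift from baseline to the worst on-treatment laboratory value, or declare its removal with a reason in SAP Section 4.

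The cost is SAP wording and some programming. The protocol already calls for these readings, so no new data collection is needed.
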